 - Hematologic intolerance: Patients with grade 3 or 4 toxicity (absolute neutrophil count [ANC] or platelets) while on therapy that is recurrent after dose reduction to the lowest doses recommended by manufacturer
6. Eastern Cooperative Oncology Group (ECOG) performance status (PS) of 0, 1, or 2
7. Adequate end organ function as defined by (as per central laboratory tests):
 - Total bilirubin $\leq 1.5 \times$ ULN except for patients with Gilbert's syndrome who may only be included if total bilirubin $\leq 3.0 \times$ ULN or direct bilirubin $\leq 1.5 \times$ ULN

- Aspartate transaminase (AST) $\leq 3.0 \times \text{ULN}$
 - Alanine transaminase (ALT) $\leq 3.0 \times \text{ULN}$
 - Serum lipase $\leq 1.5 \times \text{ULN}$. For serum lipase $> \text{ULN} - \leq 1.5 \times \text{ULN}$, value must be considered not clinically significant and not associated with risk factors for acute pancreatitis
 - Alkaline phosphatase $\leq 2.5 \times \text{ULN}$
 - Creatinine clearance $\geq 50 \text{ mL/min}$ as calculated using Cockcroft-Gault formula
8. Patients must avoid consumption of grapefruit, Seville oranges or products containing the juice of each during the entire study and preferably 7 days before the first dose of study medications, due to potential CYP3A4 interaction with the study medications. Orange juice is allowed.
9. Written informed consent obtained prior to any screening procedures.
- 10a. Patients must have the following electrolyte values (as per central laboratory tests) within normal limits or corrected to be within normal limits with supplements prior to first dose of study medication:
- Potassium (potassium increase of up to 6.0 mmol/L is acceptable at study entry if associated with creatinine clearance within normal limits)
 - Total calcium (corrected for serum albumin); (calcium increase of up to 12.5 mg/dl or 3.1 mmol/L is acceptable at study entry if associated with creatinine clearance within normal limits)
 - Magnesium, with the exception of magnesium increase $> \text{ULN} - 3.0 \text{ mg/dL}$; $> \text{ULN} - 1.23 \text{ mmol/L}$ associated with creatinine clearance (calculated using Cockcroft-Gault formula) within normal limits.
11. Evidence of typical BCR-ABL1 transcript [e14a2 and/or e13a2] at the time of screening which are amenable to standardized RQ-PCR quantification.

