> 3.0 - 5.0 x ULN	Recommendation: Maintain dose level. Repeat LFTs ^b as soon as possible, preferably within 48-72 hours from awareness of the abnormal results; if abnormal lab values are confirmed upon the repeat test, then monitor LFTs ^b weekly, or more frequently if clinically indicated, until resolved to ≤ 3.0 x ULN	Recommendation: Maintain dose level. Repeat LFTs ^b as soon as possible, preferably within 48-72 hours from awareness of the abnormal results; if abnormal lab values are confirmed upon the repeat test, then monitor LFTs ^b weekly, or more frequently if clinically indicated, until resolved to ≤ 3.0 x ULN

[figure not shown]
Dose modifications for both asciminib and bosutinib Please note that if a patient requires a dose interruption of > 28 days for each toxicity, then the patient must be discontinued from the study treatment		
Worst toxicity CTCAE Grade 4.03	Asciminib	Bosutinib
> 5.0 - 10.0 x ULN	Mandatory: Hold dose. Repeat LFTs ^b as soon as possible, preferably within 48-72 hours from awareness of the abnormal results; monitor LFTs ^b weekly, or more frequently if clinically indicated, until resolved to ≤ 3.0 x ULN: Then If resolved in ≤ 14 days, maintain dose level If resolved in > 14 days, reduce dose ↓ 1 dose level	Mandatory: Hold dose. Repeat LFTs ^b as soon as possible, preferably within 48-72 hours from awareness of the abnormal results; monitor LFTs ^b weekly, or more frequently if clinically indicated, until resolved to ≤ 2.5 x ULN: Then Recommendation: If resolved in ≤ 28 days, reduce dose ↓ 1 dose level Recommendation: If resolved in > 28 days, Discontinue patient from study drug treatment
> 10.0 - 20.0 x ULN	Mandatory: Hold dose. Repeat LFTs ^b as soon as possible, preferably within 48-72 hours from awareness of the abnormal results; monitor LFTs ^b weekly, or more frequently if clinically indicated, until resolved to ≤ baseline. Then reduce dose ↓ 1 dose level.	Mandatory: Hold dose. Repeat LFTs ^b as soon as possible, preferably within 48-72 hours from awareness of the abnormal results; monitor LFTs ^b weekly, or more frequently if clinically indicated, until resolved to ≤ 2.5 x ULN. Then Recommendation: If resolved in ≤ 28 days, reduce dose ↓ 1 dose level maintain dose level Recommendation: If resolved in > 28 days, Discontinue patient from study drug treatment.

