> 20.0 x ULN	Mandatory: Hold dose. Repeat LFTs ^b as soon as possible, preferably within 48-72 hours from awareness of the abnormal results; monitor LFTs ^b weekly, or more frequently if clinically indicated, until resolved to ≤ 3 x ULN (or ≤ 5 x ULN for patients with baseline value > 3.0 -5.0 x ULN), then resume treatment at reduce dose ↓ 1 dose level. Only 1 dose reduction is allowed; if reoccurs at > 5 x ULN, discontinue patient from study drug treatment.	Mandatory: Hold dose. Repeat LFTs ^b as soon as possible, preferably within 48-72 hours from awareness of the abnormal results; monitor LFTs ^b weekly, or more frequently if clinically indicated, until resolved to ≤ 2.5 x ULN (then Recommendation: If resolved in ≤ 28 days, reduce dose ↓ 1 dose level maintain dose level Recommendation: If resolved in > 28 days, Discontinue patient from study drug treatment

[figure not shown]
Dose modifications for both asciminib and bosutinib Please note that if a patient requires a dose interruption of > 28 days for each toxicity, then the patient must be discontinued from the study treatment		
Worst toxicity CTCAE Grade 4.03	Asciminib	Bosutinib
Combined ^c elevations of AST or ALT and total bilirubin		
For patients with normal baseline ALT and AST and total bilirubin value: AST or ALT >3.0 x ULN combined with total bilirubin >2.0 x ULN without evidence of cholestasis ^d For patients with elevated baseline AST or ALT or total bilirubin value [AST or ALT >2 x baseline AND > 3.0 x ULN]	Mandatory: Permanently discontinue patient from study drug treatment. Repeat as soon as possible, preferably within 48 hours from awareness of the abnormal results, then with weekly monitoring of LFTs ^b), or more frequently if clinically indicated, until AST, ALT, or bilirubin have resolved to baseline or stabilization over 4 weeks. Refer to Section 6.3.3.1 for additional follow-up evaluations as applicable.	Mandatory: Permanently discontinue patient from study drug treatment. Repeat as soon as possible, preferably within 48 hours from awareness of the abnormal results, then with weekly monitoring of LFTs ^b), or more frequently if clinically indicated, until AST, ALT, or bilirubin have resolved to baseline or stabilization over 4 weeks. Refer to Section 6.3.3.1 for additional follow-up evaluations as applicable.
Investigation (metabolic)		
Asymptomatic amylase and/or lipase elevation		

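### Table 6-2 sets a stricter asciminib restart level after an AST/ALT peak of > 10-20 x ULN than after > 20 x ULN, and the > 20 row cites baselines that eligibility excludes for randomized patients

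*Combined protocol and SAP*

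**What the plan says.** All references are to the Amendment 3 protocol unless stated. Section 6.3.1, Table 6-2, isolated AST or ALT elevation, asciminib column, has three mandatory rows in which the dose is held:

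- Peak > 5-10 x ULN: hold "until resolved to ≤ 3.0 x ULN: Then If resolved in ≤ 14 days, maintain dose level"; if resolution takes longer, resume one level lower.
- Peak > 10-20 x ULN: hold "until resolved to ≤ baseline. Then reduce dose ↓ 1 dose level".
- Peak > 20 x ULN: hold "until resolved to ≤ 3 x ULN (or ≤ 5 x ULN for patients with baseline value > 3.0 -5.0 x ULN"). The 5 x ULN limit is thus "for patients with baseline value > 3.0 -5.0 x ULN), then resume treatment at reduce dose", that is, one level lower. This row also allows only one reduction and requires discontinuation if the elevation returns above 5 x ULN.

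Section 5.2, inclusion criterion 7, caps both AST and ALT at 3.0 x ULN by central laboratory. Section 7.1.2 and Table 7-1 treat the screening assessment as baseline.

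Patients who fail bosutinib and switch to asciminib have a separate baseline with chemistry (Table 7-2). The switch conditions in the protocol summary bar unresolved Grade 3 or 4 toxicity but give no AST or ALT ceiling in multiples of ULN.

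Section 6.3.1 permits no departure from rules marked mandatory. It requires discontinuation when a non-hematologic toxicity needs more than 28 days off drug.

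**The concern.** As the peak rises, the restart level runs 3.0 x ULN, then baseline, then 3 x ULN. The middle row is the odd one out: a patient with the higher peak can restart at a higher enzyme level than a patient with the lower peak, at the same reduced dose. The protocol gives no reason for this.

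The > 20 row also makes provision for a baseline that criterion 7 does not admit, so a site cannot tell which patients the provision is for.

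The rows are mandatory, so an investigator may not resolve either point by judgement. Returning fully to baseline within 28 days is a harder condition than falling to 3 x ULN. The > 10-20 row is therefore the more exposed to discontinuation under the 28-day limit.

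**Working it through.** The plan gives no figure to reproduce. The check writes each restart level as a function of the patient's baseline b (in x ULN) and compares the rows.

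Inputs, from Table 6-2 (asciminib) and Section 5.2:

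- R1, after > 5-10 x ULN: 3.0
- R2, after > 10-20 x ULN: b
- R3, after > 20 x ULN: 3.0, or 5.0 if 3.0 < b ≤ 5.0
- Eligible range for randomized patients: b ≤ 3.0

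| Baseline b | Criterion 7 | R1 | R2 | R3 | R3 − R2 |
|---|---|---|---|---|---|
| 0.5 | met | 3.0 | 0.5 | 3.0 | 2.5 |
| 1.0 | met | 3.0 | 1.0 | 3.0 | 2.0 |
| 2.0 | met | 3.0 | 2.0 | 3.0 | 1.0 |
| 2.5 | met | 3.0 | 2.5 | 3.0 | 0.5 |
| 3.0 | met | 3.0 | 3.0 | 3.0 | 0.0 |
| 4.0 | not met | 3.0 | 4.0 | 5.0 | 1.0 |
| 5.0 | not met | 3.0 | 5.0 | 5.0 | 0.0 |

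**Ordering.** For b ≤ 3.0, R3 − R2 = 3.0 − b. This is positive for every b below 3.0 and zero at 3.0. On a grid from 0.01 to 3.00 in steps of 0.01, R3 exceeds R2 at 299 of 300 points, equals it at one, and is never lower. As a ratio R3/R2, this is 3.0/1.0 = 3 at baseline 1.0, 3.0/2.0 = 1.5 at baseline 2.0, and 1 at baseline 3.0.

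**Dose.** R2 and R3 both lead to one level lower, and Table 6-3 gives asciminib only one reduced level. The dose step does not offset the difference.

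**Branch.** The ranges b ≤ 3.0 and 3.0 < b ≤ 5.0 do not overlap, so no randomized patient who meets criterion 7 at baseline can use the 5 x ULN limit. A switch patient might. The bosutinib column recommends keeping the dose at > 3.0-5.0 x ULN, and the listed switch conditions set no ceiling. At b = 4.0 such a patient would face 3.0, 4.0 and 5.0 as the peak rises, so the restart level would loosen at each step.

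**Other rules that might settle it:**

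- The table note that the worst preceding toxicity governs only selects the row.
- The general Grade 4 non-hematologic rule gives way where a specific section exists, as it does here.
- The 28-day limit applies to every row alike.
- The bosutinib column uses a single restart level, 2.5 x ULN, in all three bands, so it gives no precedent for the asciminib pattern.

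**History.** The Amendment 1 protocol in the same file already has the three rows and the same eligibility caps. Amendment 3 introduced the switch option, so the branch was not written for switch patients.

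**The case against.** The strongest reply is that each row can be carried out as written. The bands do not overlap, no patient receives two conflicting instructions, and whether restart levels should tighten with the peak is a clinical judgement. The > 20 row is also stricter in one respect: return above 5 x ULN ends treatment, whereas the general rule in Section 6.3.1 requires recurrence at the same or worse severity.

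The recurrence clause is a real safeguard, but it acts only after re-exposure. It does not explain why the restart level is easier to meet. The clinical choice does belong to the sponsor, but the protocol does not record that a choice was made.

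A reader might go further in three ways that the documents do not support:

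- *That the branch is impossible.* It conflicts with criterion 7 for randomized patients only; the switch group may fall within it. The Amendment 3 text available ends within Section 7.1.2, so its Section 7.1.2.2 on switch conditions could not be checked.
- *That these rows govern the gravest liver signal.* They cover isolated transaminase elevation. Combined elevation with bilirubin has its own row, with permanent discontinuation, and its own follow-up in Section 6.3.3.1.
- *That the ordering distorts the primary endpoint.* Scoring discontinuation before 24 weeks as non-response comes from Section 10.4.3 of the Amendment 1 protocol; the Amendment 3 version of that section was not available. No event rate is given for these bands.

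**Conclusion.** The point holds as an internal inconsistency in mandatory rules. For every eligible baseline below 3.0 x ULN, the > 10-20 row demands a lower restart level than the > 20 row. The gap is 2.0 x ULN at a baseline of 1.0, 1.0 x ULN at 2.0, and nil at 3.0. Separately, the > 3.0-5.0 x ULN branch does not fit criterion 7 for randomized patients, and its scope is unstated.

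This rests on reading baseline as the screening value. Table 7-1 also schedules chemistry on Week 1 Day 1, so a different definition of baseline would need to be stated.

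Few patients are likely to be affected. Section 1.2.1.2 does not list transaminase elevation among the events above 10% in the 35 patients treated at 40 mg BID, although the rate in these severity bands is not given. Any effect on the Week 24 response rate is unquantified and expected to be small. The case for acting rests on clear mandatory safety rules, not on bias in the comparison.

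**What to change.** Reconcile the three asciminib AST/ALT rows of Table 6-2 with each other, and state the reason if the present ordering is intended. Reconcile the > 3.0-5.0 x ULN baseline branch with inclusion criterion 7 and with the switch conditions, and say to whom it applies and which assessment counts as baseline. The restart levels, and whether the branch stays, are for the clinical team; none is proposed here.

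The cost is table wording in a protocol amendment. It needs no change to sample size, endpoint or analysis.

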6.3 Dose modifications

6.3.1 Dose modification and dose delay

[figure not shown]
For patients who do not tolerate the protocol-specified dosing schedule, dose interruptions and/or reductions are either recommended or mandated in order to allow the patient to continue the study treatment.

These dose modifications are summarized in [Table 6-2](#). The dose reduction indicated as “recommendations” are provided to assist investigators in the event the patient experiences toxicity. However, deviations from “mandatory” dose interruptions and/or reductions are not allowed and mandatory interruptions or reductions must be strictly followed. Re-escalation to asciminib 40 mg BID is permitted if a change in the patient’s individual benefit/risk assessment at the lower dose level is seen. Re-escalation will be allowed only once for any given patient on the asciminib arm per protocol. Permanent treatment discontinuation is mandatory for specific events indicated as such in [Table 6-2](#). Any dose changes must be recorded on the Dosage Administration Record eCRF.

[figure not shown]
A patient must discontinue treatment with either asciminib or bosutinib if, after treatment is resumed at a lower dose level, the toxicity recurs with the same or worse severity, except for recurrence of cytopenias ([Table 6-2](#)). If a patient requires a dose interruption of > 28 days for each non-hematologic toxicity, then the patient must be discontinued from the study treatment. If a hematologic toxicity (cytopenia Grade 3 or 4) lasts for more than 42 days without recovery to at least a Grade 2, despite TKI interruption and adequate management (including hematopoietic growth factors), then the patient must be discontinued from the study treatment.

Table 6-2 Criteria for dose reduction/interruption and re-initiation of asciminib and bosutinib treatment for adverse drug reactions

[figure not shown]
Dose modifications for both asciminib and bosutinib		
Please note that if a patient requires a dose interruption of > 28 days for each toxicity, then the patient must be discontinued from the study treatment		
Worst toxicity CTCAE Grade 4.03	Asciminib	Bosutinib
Investigations (Hematologic) If a hematologic toxicity (cytopenia Grade 3 or 4) lasts for more than 42 days without recovery to at least a Grade 2, despite TKI interruption and adequate management (including hematopoietic growth factors), then the patient must be discontinued from the study treatment.		
Neutropenia (ANC)		

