Grade 1 (ANC < LLN – 1.5 x 10 ⁹ /L)	Recommendation: Maintain dose level	Recommendation: Maintain dose level
Grade 2 (ANC < 1.5 – 1.0 x 10 ⁹ /L)	Recommendation: Maintain dose level	Recommendation: Maintain dose level
Grade 3 (ANC < 1.0 – 0.5 x 10 ⁹ /L)	Mandatory: Hold dose until resolved to ≤ Grade 2 (recheck CBC 2x/week), then: if resolved in ≤ 14 days, then maintain dose level If resolved in > 14 days, then reduce dose ↓ 1 dose level	Mandatory: Hold dose until resolved to ≤ Grade 2 and platelets ≤ Grade 2 (recheck CBC 2x/week), then: if resolved in ≤ 14 days, then maintain dose level If resolved in > 14 days, reduce dose ↓ 1 dose level
Grade 4 (ANC < 0.5 x 10 ⁹ /L)	Mandatory: Hold dose until resolved to ≤ Grade 2, (recheck CBC 2x/week), then: if resolved in ≤ 14 days, then maintain dose level if resolved in > 14 days, then reduce dose ↓ 1 dose level	Mandatory: Hold dose until resolved to ≤ Grade 2 and platelets ≤ Grade 2 (recheck CBC 2x/week), then: if resolved in ≤ 14 days, then maintain dose level if resolved in > 14 days, then reduce dose ↓ 1 dose level
Febrile neutropenia (ANC < 1.0 x 10 ⁹ /L, fever ≥ 38.5°C)	Mandatory: Hold dose until resolved, then reduce dose ↓ 1 dose level	Mandatory: Hold dose until resolved, then reduce dose ↓ 1 dose level
Thrombocytopenia		
Grade 1 (PLT < LLN – 75 X 10 ⁹ /L)	Recommendation: Maintain dose level	Recommendation: Maintain dose level
Grade 2 (PLT < 75 - 50 x 10 ⁹ /L)	Recommendation: Maintain dose level	Recommendation: Maintain dose level

[figure not shown]
Dose modifications for both asciminib and bosutinib		
Please note that if a patient requires a dose interruption of > 28 days for each toxicity, then the patient must be discontinued from the study treatment		
Worst toxicity CTCAE Grade 4.03	Asciminib	Bosutinib
Grade 3 (PLT < 50 - 25 x 10 ⁹ /L)	Mandatory: Hold dose until resolved to ≤ Grade 2 (recheck CBC 2x/week), then: if resolved in ≤ 14 days, then maintain dose level if resolved in > 14 days, then reduce dose ↓ 1 dose level	Mandatory: Hold dose until resolved to ≤ Grade 2 and neutrophils ≤ Grade 2 (recheck CBC 2x/week), then: if resolved in ≤ 14 days, then maintain dose level if resolved in > 14 days, then reduce dose ↓ 1 dose level

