Grade 1 (> ULN - 1.5 x ULN)	Recommendation: Maintain dose level, measure 2x week	Recommendation: Maintain dose level, measure 2x week
Grade 2 (> 1.5 - 2.0 x ULN)	Recommendation: Maintain dose level, measure 2x week	Recommendation: Maintain dose level, measure 2x week
Grade 3 (> 2.0 - 5.0 x ULN)	Mandatory: Hold dose until resolved to Grade ≤ 1 or baseline, then: If resolved in ≤ 7 days, then reduce dose ↓ 1 dose level If resolved in > 7 days, then discontinue treatment and obtain appropriate imaging (i.e., MRI, CT scan or ultrasound).	Mandatory: Hold dose until resolved to Grade ≤ 1 or baseline, then: If resolved in ≤ 7 days, then reduce dose ↓ 1 dose level If resolved in > 7 days, then discontinue treatment and obtain appropriate imaging (i.e., MRI, CT scan or ultrasound).
Grade 4 (> 5.0 x ULN)	Mandatory: Permanently discontinue patient from study drug treatment. Obtain appropriate imaging (i.e., MRI, CT scan or ultrasound).	Mandatory: Permanently discontinue patient from study drug treatment. Obtain appropriate imaging (i.e., MRI, CT scan or ultrasound).

Dose modifications for both asciminib and bosutinib		
Please note that if a patient requires a dose interruption of > 28 days for each toxicity, then the patient must be discontinued from the study treatment		
Worst toxicity CTCAE Grade 4.03	Asciminib	Bosutinib
Vascular disorders		
Hypertension		
CTCAE Grade 3	Mandatory: Hold dose until resolved \leq Grade 1, then reduce dose \downarrow 1 dose level	Mandatory: Hold dose until resolved \leq Grade 1, then reduce dose \downarrow 1 dose level
CTCAE Grade 4	Mandatory: Permanently discontinue patient from study drug treatment.	Mandatory: Permanently discontinue patient from study drug treatment.
Gastro intestinal		
Pancreatitis		

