Grade 2 (radiologic findings for pancreatitis as per CTCAE v4.03, for increased enzymes please see table for asymptomatic amylase and/or lipase elevation)	Mandatory: If asymptomatic radiologic pancreatitis, hold treatment until recovery of the radiologic findings. If treatment delay is \leq 21 days, then reduce dose \downarrow 1 dose level. If treatment delay > 21 days, discontinue treatment and keep monitoring with appropriate imaging (i.e., MRI, CT scan or ultrasound).	Mandatory: If asymptomatic radiologic pancreatitis, hold treatment until recovery of the radiologic findings. If treatment delay is \leq 21 days, then reduce dose \downarrow 1 dose level. If treatment delay > 21 days, discontinue treatment and keep monitoring with appropriate imaging (i.e., MRI, CT scan or ultrasound).
Grade \geq 3	Mandatory: Permanently discontinue patient from study drug treatment. Obtain appropriate imaging (i.e., MRI, CT scan or ultrasound).	Mandatory: Permanently discontinue patient from study drug treatment. Obtain appropriate imaging (i.e., MRI, CT scan or ultrasound).
Diarrhea***		
Grade 1	Recommendation: Maintain dose level but, initiate anti-diarrhea treatment	Recommendation: Maintain dose level but, initiate anti-diarrhea treatment
Grade 2	Recommendation: Hold dose until resolved to \leq grade 1, then maintain dose level. If diarrhea returns as \geq grade 2, then hold dose until resolved to \leq grade 1, then reduce dose \downarrow 1 dose level	Recommendation: Hold dose until resolved to \leq grade 1, then maintain dose level. If diarrhea returns as \geq grade 2, then hold dose until resolved to \leq grade 1, then reduce dose \downarrow 1 dose level
Grade 3	Recommendation: Hold dose and discontinue patient from study drug treatment	Mandatory: Hold dose until recovery to \leq grade 1. Recommendation: Bosutinib may then be resumed at \downarrow 1 dose level
Grade 4	Mandatory: Permanently discontinue patient from study drug treatment	Mandatory: Hold dose until recovery to \leq grade 1. Recommendation: Bosutinib may then be resumed at \downarrow 1 dose level

Dose modifications for both asciminib and bosutinib		
Please note that if a patient requires a dose interruption of > 28 days for each toxicity, then the patient must be discontinued from the study treatment		
Worst toxicity CTCAE Grade 4.03	Asciminib	Bosutinib
Skin and subcutaneous tissue disorders		
Rash/photosensitivity		

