Dose modifications for both asciminib and bosutinib		
Please note that if a patient requires a dose interruption of > 28 days for each toxicity, then the patient must be discontinued from the study treatment		
Worst toxicity CTCAE Grade 4.03	Asciminib	Bosutinib

If combined elevations of AST or ALT and total bilirubin do not meet the defined thresholds, please follow the instructions for isolated elevation of total bilirubin and isolated elevation of AST/ALT, and take a conservative action based on the degree of the elevations (e.g. discontinue treatment at the situation when hold dose is needed for one parameter and discontinue treatment is required for another parameter). After all elevations resolve to the defined thresholds that allow treatment re-initiation, re-start the treatment either at the same dose or at one dose lower if meeting a criterion for dose reduction
 
^d “Cholestasis” defined as ALP elevation (>2.0 x ULN and R value <2) in patients without bone metastasis, or elevation of ALP liver fraction in patients with bone metastasis
 
Note: The R value is calculated by dividing the ALT by the ALP, using multiples of the ULN for both values. It denotes whether the relative pattern of ALT and/or ALP elevation is due to cholestatic (R ≤ 2), hepatocellular (R ≥ 5), or mixed (R >2 and < 5) liver injury
 
* Note: If total bilirubin > 3.0 x ULN is due to the indirect (non-conjugated) component only, and hemolysis as the etiology has been ruled out as per institutional guidelines (e.g., review of peripheral blood smear and haptoglobin determination), then ↓ 1 dose level and continue treatment at the discretion of the investigator.
 
** Note: A CT scan or other imaging study to assess the pancreas, liver, and gallbladder must be performed within 1 week of the first occurrence of any ≥ Grade 3 of amylase and/or lipase. If asymptomatic Grade 2 elevations of lipase and/or amylase occur again at the reduced dose, patients will be discontinued permanently from study treatment.
 
*** Note: antidiarrheal medication is recommended at the first sign of abdominal cramping, loose stools or overt diarrhea
		

[figure not shown]

Table 6-3 Dose reduction steps for asciminib and bosutinib

Dose reduction*			
	Starting dose level – 0	Dose level – 1	
Asciminib BID	40 mg tablet BID (total daily dose 80 mg)	20 mg tablet BID (total daily dose 40 mg)	
*Dose reduction should be based on the worst toxicity demonstrated at the last dose.			

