6.3.2 Dose adjustments for QTcF prolongation

If QTcF >500 msec or QTcF prolongation >60 msec from baseline is observed at any point during study treatment, and confirmed, the below guidance must be followed:

1. Assess the quality of the ECG recording and the QT value and repeat if needed
2. Interrupt study treatment until confirmed resolution of QTcF and as per dose reduction guidelines for non-hematological AEs.
3. Determine the serum electrolyte levels (in particular hypokalemia, hypomagnesemia). If abnormal, correct abnormalities before resuming study drug treatment.
4. Review concomitant medication associated with QT prolongation, including drugs with a “Known”, “Possible”, or “Conditional risk of Torsades de Pointes” (refer to www.crediblemeds.org/), and drugs with the potential to increase the risk of study drug exposure related QT prolongation.
5. Check study drug dosing schedule and treatment compliance.

After confirming ECG reading at site, if QTcF > 500 msec

- Interrupt study treatment
- Repeat ECG and confirm ECG diagnosis by a cardiologist or central ECG lab
- If QTcF confirmed > 500 msec:
 - Correct electrolytes, eliminate culprit concomitant treatments, and identify and address clinical conditions that could potentially prolong the QT as per the ECG and QTc Clinical Safety Standards Guidelines Section 3.3.1.
 - Consult with a cardiologist (or qualified specialist)
 - Increase cardiac monitoring as indicated, until the QTcF returns to ≤ 480 msec.
- After resolution to ≤ 480 msec, consider re-introducing treatment at reduced dose, and increase ECG monitoring for the next treatment(s), (e.g. pre-dose and 2 hours post dose after one week and two weeks of treatment re-introduction):

- If QTcF remains ≤ 500 msec after dose reduction, continue planned ECG monitoring during subsequent treatment
- If QTcF > 500 msec recurs after dose reduction, discontinue patient from trial.

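### Table 6-2 lets a patient with Grade 3 lipase or amylase elevation restart on enzyme recovery before the mandatory pancreatic scan has been read

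*Combined protocol and SAP*

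**What the plan says.** All references are to the combined protocol and SAP, Amendment 3 text, Section 6.3.1 and Table 6-2 unless stated otherwise.

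- **Grade 3 lipase/amylase row, asymptomatic, mandatory, same wording in both arms:** "Hold dose until resolved to Grade ≤ 1 or baseline, then: If resolved in ≤ 7 days, then reduce dose ↓ 1 dose level". If recovery takes longer than 7 days, treatment is discontinued and imaging obtained. Within this row, imaging is named only in that slower branch.
- **Footnote \*\*:** "A CT scan or other imaging study to assess the pancreas, liver, and gallbladder must be performed within 1 week of the first occurrence". The trigger is an amylase or lipase value of Grade 3 or higher. The footnote gives no deadline for reading the scan and does not mention restart.
- **Pancreatitis, Grade 2, mandatory, both arms:** "If asymptomatic radiologic pancreatitis, hold treatment until recovery of the radiologic findings". A reduced-dose restart follows if the delay is at most 21 days; otherwise treatment stops. This row is defined by radiologic findings and refers the reader elsewhere for enzymes: "for increased enzymes please see table for asymptomatic amylase and/or lipase elevation".
- **General rules:** dose changes follow the worst preceding toxicity (notes to Table 6-2), and mandatory holds may not be deviated from (Section 6.3.1).

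**The concern.** Two rows of one table release a hold on different evidence. The enzyme row releases on laboratory values; the Grade 2 pancreatitis row releases on imaging. The footnote supplies the scan that would move a patient from the first row to the second, but nothing says that its result must be known before the quick restart. The cross-reference also runs one way: the Pancreatitis row points to the enzyme rows, while the Grade 3 enzyme row does not point back.

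A site that follows every line can therefore restart a patient, scan later in the week, and only then find radiologic pancreatitis that called for a hold. What is at stake is a short period of dosing in a patient who should have been off drug. The pancreas is listed as a potential target organ in the toxicity studies (Section 1.2.1.1), and Section 1.2.1.2 gives increased lipase as the most common Grade 3/4 event (17.1%), in the paragraph that describes the 40 mg BID group. That shows the row is likely to be used. It does not say how many patients will recover within 7 days.

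**Working it through.** The plan states no figure on this point, so there is none to reproduce. The check is a comparison of two clocks.

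**Inputs**
- Restart day d: any day from 1 to 7 (Grade 3 enzyme row).
- Scan due: by day 7, reading one week as 7 days (footnote \*\*).
- Limit on a non-hematologic interruption: 28 days (Section 6.3.1).
- Assumption: both clocks start on day 0, the day of the first Grade 3 value, and the hold starts that day.
- Assumption: reading time r is 0 to 3 days. The documents give no value.

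**Step 1. Restart ahead of the scan.** With the scan on its last permitted day, restart comes 7 − d days before the scan and 7 − d + r days before its result.

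| Restart day d | Days before scan is due, 7 − d | Days before result, r = 0 to 3 |
|---|---|---|
| 1 | 6 | 6 to 9 |
| 3 | 4 | 4 to 7 |
| 5 | 2 | 2 to 5 |
| 7 | 0 | 0 to 3 |

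If the scan is done and read before the enzymes recover, the window is 0. These are upper limits for each d, not expected values.

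**Step 2. Does another rule close the window?** The worst-preceding-toxicity rule acts on a toxicity that is known. A scan not yet done or read has not established one, so the rule cannot act inside the window. The Grade 2 pancreatitis hold has the same limit. Both act once a positive result is read, including in a patient who has already restarted.

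**Step 3. Is there room to wait?** If restart waits for the result, its latest day is 7 + r = 7 to 10. The margin to the interruption limit is 28 − 10 = 18 to 28 − 7 = 21 days. The added delay against today's rule is 7 + r − d, which runs from 0 (d = 7, r = 0) to 9 days (d = 1, r = 3).

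**The case against.** The strongest reply is that the table already handles a positive scan. A reader might infer from the Grade 3 enzyme row that nothing in the protocol ties dosing to the scan result. The documents do not support that: the Grade 2 pancreatitis row does so, it is mandatory in both arms, and together with the worst-preceding-toxicity rule it would stop a patient who had restarted. This stands, and it confines the point to sequence.

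Nor does anything force an early restart. The 28-day limit, "If a patient requires a dose interruption of > 28 days for each non-hematologic toxicity, then the patient must be discontinued", leaves a careful site free to wait. This stands too, but the row does not ask the site to wait.

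A reader might also infer that enzyme recovery is worthless because lipase is unspecific. The Amendment 2 rationale does not say so. It notes that other conditions can raise lipase, but it prefers lipase for its sensitivity and specificity; the marker it calls non-specific is amylase. The argument here rests only on the fact that the Grade 2 pancreatitis hold is defined by imaging.

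Other safeguards reduce the risk. These patients have no symptoms and recovered enzymes, they restart one level lower, and the footnote adds: "If asymptomatic Grade 2 elevations of lipase and/or amylase occur again at the reduced dose, patients will be discontinued permanently from study treatment". The pancreatitis cases in Section 2.3 arose at 80 mg and 150 mg BID, not at 40 mg BID. All of this bears on size and leaves the ordering gap open.

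The protocol does set second restart conditions elsewhere: "Hold dose until resolved to ≤ Grade 2 and platelets ≤ Grade 2" for bosutinib neutropenia, and "If abnormal, correct abnormalities before resuming study drug treatment" in Section 6.3.2. These show that such wording fits the protocol's style. They do not amount to a general rule that this row breaks: the platelet condition is in the bosutinib column only and comes from the same blood count.

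**Conclusion.** The point holds as a gap in the order of events. Under the current wording, restart in the quick-recovery branch can precede the scan's due date by 0 to 6 days, plus reading time, and so can precede a finding that mandates a hold. The 0 to 6 days rests on both clocks starting at the first Grade 3 value and on a scan taken on the last permitted day. Any longer figure rests on the assumed reading time.

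The residual risk is modest. The number of patients affected cannot be derived from the documents, and none is claimed. The pancreatic evidence in the documents concerns asciminib; the bosutinib column is included because its row text is identical. A reader might look for a bias in the trial's results, but no endpoint or analysis depends on this row's wording.

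**What to change.** In the branch for recovery within 7 days of the Grade 3 lipase/amylase row, both columns, write:

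*If enzymes resolve in ≤ 7 days, resume at one dose level lower only after the imaging required by footnote \*\* has been done and read and shows no pancreatitis; otherwise follow the Pancreatitis rows. The 7-day limit refers to enzyme recovery only.*

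The last sentence is needed so that a patient with recovered enzymes is not discontinued merely because the report is pending. Leave the existing instruction for slower recovery as it is.

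This is a wording change in a protocol amendment. It adds no procedure, because the scan is already required, and it removes no safeguard. The price is a possible restart delay of some days while the scan is done and read, which sites can shorten by scanning early.
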